#### Assessment

All AEs must be evaluated by an Investigator as to:

- **Seriousness:** whether the AE is an SAE. See above for the seriousness criteria.
- **Severity:**

- Severity must be evaluated by an Investigator according to the following definitions:
  - *Mild* – no or transient symptoms, no interference with the subject's daily activities
  - *Moderate* – marked symptoms, moderate interference with the subject's daily activities
  - *Severe* – considerable interference with the subject's daily activities, unacceptable
- **Causality:**

Not related	
Relationship to the device, comparator or procedures can be excluded when:
 
 
- the event has no temporal relationship with the use of the investigational device, or the procedures related to application of the investigational device
 
- the serious adverse event does not follow a known response pattern to the medical device (if the response pattern is previously known) and is biologically implausible;
 
- the discontinuation of medical device application or the reduction of the level of activation/exposure - when clinically feasible - and reintroduction of its use (or increase of the level of activation/exposure), do not impact on the serious adverse event;
 
- the event involves a body-site or an organ that cannot be affected by the device or procedure;
 
- the serious adverse event can be attributed to another cause (e.g. an underlying or concurrent illness/ clinical condition, an effect of another device, drug, treatment or other risk factors);
 
- the event does not depend on a false result given by the investigational device used for diagnosis, when applicable;
 
 
In order to establish the non-relatedness, not all the criteria listed above might be met at the same time, depending on the type of device/procedures and the serious adverse event.

Possible	The relationship with the use of the investigational device or comparator, or the relationship with procedures, is weak but cannot be ruled out completely. Alternative causes are also possible (e.g. an underlying or concurrent illness/ clinical condition or/and an effect of another device, drug or treatment). Cases where relatedness cannot be assessed, or no information has been obtained should also be classified as possible.
Probable	The relationship with the use of the investigational device or comparator, or the relationship with procedures, seems relevant and/or the event cannot be reasonably explained by another cause.

Causal relationship	
The serious adverse event is associated with the investigational device, comparator or with procedures beyond reasonable doubt when:
 
 
- the event is a known side effect of the product category the device belongs to or of similar devices and procedures;
 
- the event has a temporal relationship with investigational device use/application or procedures;
 
- the event involves a body-site or organ that 
 
• the investigational device or procedures are applied to;
 
• the investigational device or procedures have an effect on;
 
 
 
- the serious adverse event follows a known response pattern to the medical device (if the response pattern is previously known);
 
- the discontinuation of medical device application (or reduction of the level of activation/exposure) and reintroduction of its use (or increase of the level of activation/exposure), impact on the serious adverse event (when clinically feasible);
 
- other possible causes (e.g., an underlying or concurrent illness/clinical condition or/and an effect of another device, drug or treatment) have been adequately ruled out;
 
- harm to the subject is due to error in use;
 
- the event depends on a false result given by the investigational device used for diagnosis, when applicable;
 
 
In order to establish the relatedness, not all the criteria listed above might be met at the same time, depending on the type of device/procedures and the serious adverse event.

----------------------------	---

### Timelines for reporting

- After informed consent has been obtained but prior to first use of the IMD, only adverse events caused by a study specific procedure should be reported
- After first use of the IMD, adverse events will be reported as follows:
  - All AEs, SAEs, AESIs and Device Deficiencies will be reported until 7 days after last use of IMD or until last follow-up visit (whichever occurs first)

All SAEs and AESI as defined in the protocol must be reported to the Sponsor within 24 hours of the trial staff becoming aware of the event. The immediate report shall be followed by detailed, written reports. The immediate and follow-up reports shall identify subjects by code numbers.

SAE details will be reported by the Investigator to the sponsor:

- By completing a paper SAE form and sending it to the following email address:  
Mail: [contact]

If an authorised Investigator from the reporting site is unavailable, initial reports without causality assessment should be submitted to the Sponsor by a healthcare professional within 24 hours of becoming aware of the SAE, but must be followed-up by medical assessment as soon as possible thereafter.

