## Criteria and procedures for subject withdrawal or loss to follow up

*When and how to withdraw a subject from the clinical investigation or stop the use of the investigational device*

Clients participate in this study voluntarily and have the right to withdraw from the study at any time they want. If they choose to withdraw they will be asked to delete the ALICE app from their smartphone or tablet.

[figure not shown]
*Documentation of efforts to be made to trace subjects that are lost to follow up and possible reasons*  
When clients withdraw from the study, they will be asked to provide a reason as this may be of interest to the study. However, they are not obligated to provide a reason for their withdrawal.

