#### *Enrolment of clients*

- Clients who match the criteria, will receive a brief introduction about the study, which may or may not include the ALICE app. If they are interested to participate in the study, they will receive an information brochure about the study programme, in which a more detailed description is provided (details about the course of the study, the 2 visits (at 0 and 8 weeks), the duration of the study and their rights and responsibilities.) They will also be informed that they will be assigned randomly to one of the two groups.
- If clients agree to participate in the study they will sign an informed consent form.
- A complete list of clients who wish to participate for each investigational site is sent to the KU Leuven researchers at the end of the recruitment period.
- After being stratified by age clients will be randomly assigned to one of the two groups by a KU Leuven researcher using an automatic seed generator:
  - 1 group will receive the standard of care

- 1 group will receive the standard of care with additional support of the ALICE app

	Responsible	Accountable
Clients match the criteria	Local PI	KUL PI
Clients get a brief introduction about the app and the goals of the study; when interested they receive a detailed information brochure	Local PI	
Clients sign an Informed Consent	Local PI	KUL PI
Clients are enrolled in the study	Local PI	KUL PI
Allocation of groups and randomization	KUL PI	KUL PI

*The study program and test protocol*

- Onboarding procedure: once the clients are enrolled they will receive a standard onboarding procedure, which will be led by the local PI. Within this procedure following points/formalities will be discussed with their client:
  - The study programme/course of the study
  - Appointment schedule to perform the tests
  - Procedure to follow in case of change
  - Contact information in case of questions
  - Risk & Safety management (see safety section), with special attention to following procedures:
    - Procedure to control the loudness of the stimuli provided by the app
    - Procedure to follow to ensure safe data management (compliant with GDPR)
    - Procedure to follow in case of adverse events and/or device malfunction
    - Rights and responsibilities
- Installation of the app
  - Intended use of the app
  - Compatibility of the app with personal (streaming) devices,
  - Instruction to use the app
  - First installation and set-up of account
- Test protocol (see below and Fig. 4)

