*Description of all the clinical-investigation-related procedures that subjects undergo during the clinical investigation including any deviation from normal clinical practice*

Below, the timeline of the test protocol is presented: After allocation to a treatment group, a client will be assessed with speech in noise and questionnaires (Figure 4), followed by 8 weeks use of the ALICE app. The same outcome measures will be assessed at the final appointment to evaluate the benefit of the intervention.

[figure not shown]

Figure 4. Timeline of the test protocol.

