#### *Enrolment of clients*

- Clients who match the criteria, will receive a brief introduction about the study, which may or may not include the ALICE app. If they are interested to participate in the study, they will receive an information brochure about the study program, in which a more detailed description is provided (details about the course of the study, the 2 visits at 0 and 8 weeks, the duration of the study and their rights and responsibilities). They will also be informed that they will be assigned randomly to one of the three groups.
- If clients agree to participate in the study they will sign an informed consent form.
- A complete list of clients who wish to participate for each investigational site is sent to the KU Leuven researchers at the end of the recruitment period.
- After being stratified by age, clients will be randomly assigned to one of the two groups by a KU Leuven researcher using an automatic seed generator:
  - 1 group will receive the standard of care
  - 1 group will receive the standard of care with additional support of the ALICE app (French version)

	Responsible	Accountable
Clients match the criteria	Local PI	KUL PI
Clients get a brief introduction about the app and the goals of the study; when interested they receive a detailed information brochure	Local PI	
Clients sign an Informed Consent Form	Local PI	KUL PI
Clients are enrolled in the study	Local PI	KUL PI
Allocation of groups and randomization	KUL PI	KUL PI

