### 3.5.14.3. Recording and reporting of Adverse Events

Investigators will seek information on AEs during each patient contact. All events, whether reported by the patient or noted by trial staff, will be recorded in the patient's medical record and in the (e)CRF within a reasonable time after becoming aware. If available, the diagnosis should be reported on the AE form, rather than the individual signs or symptoms. If no diagnosis is available, the Investigator should record each sign and symptom as individual AEs using separate AE forms.

The following minimum information should be recorded for each AE:

- AE description
- start and stop date of the AE
- severity
- seriousness
- causality assessment to the Investigational Medical Device (IMD) and/or study procedures
- outcome
- what caused the AE
- possible solution

Possible adverse events that may occur during this study:

- The test used in the clinical protocol are standard clinical tests used in daily practice. These tests do not hold any risks for the participants in the study.
- Use of the training app can lead to a high cognitive load, which can result in feelings of fatigue.

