### Follow-up

The Investigator must record follow-up information by updating the patient's medical records and the appropriate forms in the (e)CRF. The worst case severity and seriousness of an event must be kept throughout the trial.

SAE follow-up information should only include new (e.g. corrections or additional) information and must be reported within 24 hours of the Investigator's first knowledge of the information. This is also the case for previously non-serious AEs which subsequently become SAEs.

- All SAEs must be followed up until the outcome of the event is 'recovered', 'recovered with sequelae', 'not recovered' (in case of death due to another cause) or 'death' (due to the SAE) and until all related queries have been resolved, or until end of trial (whichever occurs first).
- *Non-serious AEs* must be followed up until the patient's last study visit, and until all related queries have been resolved.

**SAEs after the end of the trial:** If the Investigator becomes aware of an SAE with suspected causal relationship to the IMD or experiment after the subject has ended the trial, the Investigator should report this SAE within the same timelines as for SAEs during the trial.

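### For app users, safety reporting closes at the earlier of 7 days after last use and the last visit, so clients who stop early have a gap before the final visit, and the cut-off conflicts with other safety sections

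*Combined protocol and SAP*

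**What the plan says.** Section 3.5.14.3, Timelines for reporting, sets one window for app users. After first use, all AEs, SAEs, AESIs and device deficiencies fall under it: they "will be reported until 7 days after last use of IMD or until last follow-up visit (whichever occurs first"). This point concerns that window only; it does not concern the standard-of-care group.

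The visit schedule gives the rule its effect. ARM 1 (3.5.6.2) describes "the 2 visits (at 0 and 8 weeks") and assessment "followed by 8 weeks use of the ALICE app". ARM 3 (3.5.6.4) likewise has "the 2 visits at 0 and 8 weeks" and 8 weeks of use. Planned last use and the final visit therefore nearly coincide.

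Other safety text is wider:

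- 3.5.14.3, Recording and reporting: "Investigators will seek information on AEs during each patient contact", and every event goes into the medical record and the (e)CRF.
- 3.5.14.4: each device deficiency is documented and reported to the sponsor, with no closing date.
- 3.5.14.5: the investigator is responsible for all safety events being recorded and reported, again with no closing date.
- 3.5.14.3, Follow-up: an SAE with suspected causality stays reportable once the subject has ended the trial. Non-serious AEs "must be followed up until the patient's last study visit, and until all related queries have been resolved".
- 3.5.14.3, Death: all deaths are reported, whatever the cause.

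**The concern.** Because the earlier date governs, the 7-day clause can never carry reporting past the last visit. It can only close reporting before that visit. Two kinds of app user are affected.

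A client who stops the app but remains in the trial leaves the window 7 days later, although the final visit may be weeks away and the investigator must ask about AEs at that visit. A client who uses the app up to the final visit leaves the window at that visit, with no days after last use.

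At stake is a consistent safety record for a pre-market investigation of a device without a CE mark. Under the recording rule a site would enter a week-6 event in an early stopper; under the timeline rule it need not report it. Two sites could both follow the plan and produce different event counts.

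**Working it through.** The plan gives no figure to reproduce, so the check is date arithmetic followed by a comparison of sections.

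**Inputs.** Last visit *V* = 56 days in ARMs 1 and 3 (visits at 0 and 8 weeks). Last use is day *s*. The values of *s* are illustrative, because the plan gives no discontinuation rate. Clients who withdraw fully are outside the calculation: 3.5.13 has no new data collected from them.

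**Formulas.**

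- Window closes at min(*s* + 7, *V*).
- Uncovered days before the final visit = max(0, *V* − *s* − 7).
- Days covered after last use = min(7, *V* − *s*).

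| Last use (day) | Window closes (day) | Uncovered of 56 days | Days covered after last use |
|---|---|---|---|
| 14 | 21 | 35 (62.5%) | 7 |
| 21 | 28 | 28 (50.0%) | 7 |
| 28 | 35 | 21 (37.5%) | 7 |
| 42 | 49 | 7 (12.5%) | 7 |
| 49 | 56 | 0 | 7 |
| 52 | 56 | 0 | 4 |
| 56 | 56 | 0 | 0 |

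More than half of follow-up is uncovered when 56 − *s* − 7 > 28, that is, when *s* < 21.

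**ARM 2.** Its visit days are in a figure that is not shown. If *V* is assumed to be 28 to 42 days, from the planned 4 to 6 weeks of use, the same threshold is *s* < 28/2 − 7 = 7 to *s* < 42/2 − 7 = 14. No conclusion here rests on ARM 2.

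**If the later date governed.** The window would close at max(*s* + 7, *V*). Last use on day 14 would be covered to day 56 instead of day 21, and last use on day 56 to day 63 instead of day 56. No app user who stays in the trial would have a gap before the final visit.

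**Do other sections close the gap?**

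- The post-trial SAE rule starts only when the subject has ended the trial, so it does not reach an early stopper who is still enrolled. It covers only SAEs with suspected causality.
- The follow-up rule for non-serious AEs concerns events already known, not new onsets.
- The death rule covers deaths only.
- The recording rule and sections 3.5.14.4 and 3.5.14.5 carry no cut-off, so they conflict with the timeline rule and do not settle which applies. The overview table in 3.5.14.5 refers AE timing back to the protocol.
- Section 3.5.14.2 says that all AEs and SAEs are to be reported, but it says so under a list of events not counted as AEs, just before text that excludes such events from reporting to the sponsor. It cannot be relied on to override the timeline rule.

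**The case against.** A reader might infer that clients stop because of fatigue or discomfort, and that the rule therefore hides those events and understates the app group's counts. The documents do not support this. An event that makes a client stop begins at or before last use, inside the window, and 7 further days follow. Discomfort from loud stimuli needs app use, and resumed use moves the last-use date forward. This objection stands, taking onset date as the governing date, which the section does not state.

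A reader might also infer that early stoppers go unreported for most of follow-up. In the 8-week arms that is true only for last use before day 21. Nor are device deficiencies simply left out: 3.5.14.4 requires each one to be reported without a time limit. The plan is inconsistent here, not silent.

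Continued app use after the final visit is likewise only a possibility. The withdrawal section says of clients "If they choose to withdraw they will be asked to delete the ALICE app from their smartphone or tablet", and no equivalent request is made of completers. But 3.5.2.6 and 3.5.11 restrict access to enrolled subjects, and nothing says that access continues.

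The defence can add that exposure plus 7 days is a recognisable window for an app whose potential harms the plan calls negligible (3.5.4.2) and whose predecessor trial reported no adverse events (3.5.3.1). That keeps the point modest. It does not explain why events that investigators must already seek and record at the final visit should fall outside reporting.

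Finally, merely switching to the later date could leave an open-ended window if access continued. No scheduled contact would stand behind it, and it could run past the default end of the investigation in 3.5.16. This stands, and the fix has to deal with it.

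**Conclusion.** The point holds in limited form. The timeline rule truncates reporting for app users who stop but stay in the trial: in the 8-week arms by 35, 21 or 7 of 56 days for last use on day 14, 28 or 42, and by nothing from day 49. A client who uses the app up to the final visit gets no post-use period, apart from suspected-related SAEs and deaths; one whose last use is some days earlier gets part or all of the 7 days.

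What is lost is mainly late-onset or off-device events. These are days outside the window, not a count of missed events, and without a discontinuation rate the number of clients affected cannot be estimated. The more certain defect is the conflict between the timeline rule and the recording rule, 3.5.14.4 and 3.5.14.5, which allows sites to handle the same event differently. It is worth correcting because it is a stated rule that removes safety data and costs almost nothing to change.

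**What to change.** 1. In 3.5.14.3, Timelines for reporting, let the later of the two dates govern, so that every app user who remains in the trial is reported at least until the last follow-up visit, whenever use stopped. State that onset date decides whether an event is inside the window.
2. Bound the period after the visit. State that study access to the app ends at the final visit, and that events in the following 7 days are reported if the client or the site raises them. This needs no extra scheduled contact.
3. Reconcile 3.5.14.2, all parts of 3.5.14.3, 3.5.14.4 and 3.5.14.5 on when reporting closes, so that recording and reporting follow one rule.

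Cost: a short amendment to the safety section, a few more non-serious events to process, and a brief reporting instruction at the final visit. If the last subject's 7 days run past that subject's last visit, the text should say how this fits the end of the investigation in 3.5.16.

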### Follow-up

The Investigator must record follow-up information by updating the patient's medical records and the appropriate forms in the (e)CRF. The worst case severity and seriousness of an event must be kept throughout the trial.

SAE follow-up information should only include new (e.g. corrections or additional) information and must be reported within 24 hours of the Investigator's first knowledge of the information. This is also the case for previously non-serious AEs which subsequently become SAEs.

- All SAEs must be followed up until the outcome of the event is 'recovered', 'recovered with sequelae', 'not recovered' (in case of death due to another cause) or 'death' (due to the SAE) and until all related queries have been resolved, or until end of trial (whichever occurs first).
- *Non-serious AEs* must be followed up until the patient's last study visit, and until all related queries have been resolved.

**SAEs after the end of the trial:** If the Investigator becomes aware of an SAE with suspected causal relationship to the IMD or experiment after the subject has ended the trial, the Investigator should report this SAE within the same timelines as for SAEs during the trial.

### Pregnancy

Female subjects must be instructed to notify the Investigator immediately if they become pregnant during the trial.

### Death

All deaths will be reported without delay to the sponsor (irrespective of whether the death is related to disease progression, the IMD, study procedure or is an unrelated event). The sponsor will notify all deaths as soon as possible after becoming aware to the EC and provide additional information if requested.

#### 3.5.14.4. Recording and reporting of Device Deficiencies

**Each Device Deficiency must be documented by the Investigator in the source documents and reported to the Sponsor on a Device Deficiency form.**

If the Device Deficiency lead to the occurrence of a (S)ADE, the (S)ADE must also be reported by the Investigator to the Sponsor on the appropriate forms and within the specified timelines.

#### 3.5.14.5. Reporting requirements to Ethics Committees (ECs) and Competent Authorities (CAs)

The Investigator is responsible for ensuring that all safety events are recorded in the (e)CRF and reported to the Sponsor in accordance with instructions provided below.

The Sponsor will promptly evaluate all SAEs, AESIs and Device Deficiencies against medical experience to identify and expeditiously communicate possible new safety findings to Investigators, ECs and applicable CA's based on applicable legislation.

